### 8.4. Age Imputation

Imputation rule for age as full date of birth is not collected in eCRF:

- Month and year of birth is available from eCRF/IRT data.
- Since the day of the birthdate is not collected then a '01' will be used for the day.

This document is confidential.

SAP Version: SAP V1.0 23-Jan-2025

Controlled Document ID: CC Effective Date 31-Aug-2020

Sponsor: GlaxoSmithKline Research & Development Limited; Protocol No.: 214066/Protocol Amendment 02

#### 8.5. **Visit Windows**

The visits recorded in study database will be used for all analyses. There is no plan to reassign visits based on actual visit dates where the visit designations documented in EDC will be used for analysis.

#### 8.6. **Pooling of Centers**

This study was planned to be conducted at approximately 60 sites in 15 countries. All data will be combined for summaries and analyses.

This document is confidential.

SAP Version: SAP V1.0 23-Jan-2025

Controlled Document ID: CCI Filing requirements: TMF Effective Date 31-Aug-2020

Page 29 of 59

Statistical Analysis Plan for Interventional Studies

Sponsor: GlaxoSmithKline Research & Development Limited; Protocol No.: 214066/Protocol Amendment 02

# 9. Demographic, Other Baseline Characteristics and Medication

# 9.1. Participant Disposition and Withdrawals

The numbers of participants screened, the numbers and percentages of screen failures, and enrolled will be summarized for each sub-trial (D/ND). The denominators for the percentages are the total number of participants screened. For all screen failed participants, reasons for screen failures will be displayed in a listing. In the event of multiple screening attempts, the final screening screen status and reasons for screen failures, if applicable, will be used for summary.

The numbers and percentages of participants who discontinue study treatment, who are withdrawn from the study early and who complete the study will be summarized for each sub-trial (D/ND). Primary reasons for study treatment discontinuation and early study withdrawals will be summarized. The denominators for the above percentages are the numbers of participants enrolled within each sub-trial (D/ND). All relevant data will be displayed in listings.

Enrolled participants with any inclusion and exclusion criteria deviations will be displayed in a listing for each sub-trial.

### 9.2. Protocol Deviations

Protocol deviation management at Column is detailed in Protocol Deviation and Non-compliance Management Column. For details on the process for defining analysis datasets refer to Data Review and Definition of Analysis Sets, see SOP Column. All participant data will be reviewed for the occurrence of protocol deviations. Identified protocol deviations will be recorded in the Clinical Trial Management System (CTMS). All deviations will be categorized as important or not important. All protocol deviations (both important and not important) will be displayed in a listing for each sub-trial (D/ND). Because most analyses will be based on the Safety Set, no participants will be excluded from reporting due to protocol deviations.

This document is confidential.

30

SAP Version: SAP V1.0 23-Jan-2025

Controlled Document ID: CC Effective Date 31-Aug-2020

Page 30 of 59

Statistical Analysis Plan for Interventional Studies

Sponsor: GlaxoSmithKline Research & Development Limited; Protocol No.: 214066/Protocol Amendment 02

# 9.3. Demographic and Baseline Characteristics

Demographic and other baseline characteristics will be summarized in a table and displayed in a listing for the Safety Set for each sub-trial (D/ND), including the following variables:

- Age at enrollment (years)
- Sex (male, female)
- Ethnicity (Hispanic or Latino, Not Hispanic or Latino, Unknown)
- High level race (American Indian or Alaska Native, Asian, Black or African American, Native Hawaiian or Other Pacific Islander, White, Unknown)
- Race detail (American Indian or Alaska Native, Asian Central/South Asian Heritage, Asian –
  East Asian Heritage, Asian Japanese Heritage, Asian South East Asian Heritage, Black or
  African American, Native Hawaiian or Other Pacific Islander, White Arabic/North African
  Heritage, White White/Caucasian/European Heritage, Unknown)
- · Height at screening (in cm)
- Weight at screening (in kg)
- Body Mass Index (BMI) (in kg/m²) calculated as Weight (kg) / [Height (m)²]

### 9.4. Baseline Disease Characteristics

The following baseline disease characteristics will be displayed in a listing for the Safety Set for each subtrial (D/ND):

- Type of dialysis (hemodialysis, peritoneal dialysis) for D participants only
- Use of iron supplements (Yes, No)
- ESA usage at enrollment (ESA user, ESA non-user)
  - ESA type for ESA users, including epoetin or an analogue, darbepoetin alfa, methoxy polyethylene glycol (PEG)-epoetin beta / continuous erythropoietin receptor activator [CERA] / epoetin beta pegol
- Standardized ESA dosage in epoetin IV U/week for ESA users, where the conversion formulas between different drugs are given below:
  - Standard ESA intravenous (IV) dose (U/week) = 161/113 × (epoetin subcutaneous dose (units)) / frequency
  - Epoetin IV: darbepoetin alfa = 250U: 1µg
  - Darbepoetin alfa: methoxy Polyethylene Glycol-epoetin beta = 1 : 1.2μg
  - Epoetin IV: methoxy PEG-epoetin beta = 208 U : 1μg
- eGFR at screening (mL/min/1.73m^2)
- Hgb at screening (g/dL)
- Hgb category at screening (<10g/dL, 10-12g/dL, >12g/dL)
- Primary CKD Etiology (congenital abnormalities of the kidney and urinary tract [CAKUT], inflammatory, other)
  - CAKUT: congenital renal disease, congenital obstructive uropathy, congenital reflux nephropathy, other
  - Inflammatory: glomerulonephritis, interstitial nephritis, pyelonephritis, secondary to autoimmune disease, acute kidney injury (e.g., drug related, sepsis, pre-renal), inflammatory cause of failed kidney transplant, other.

This document is confidential.

SAP Version: SAP V1.0 23-Jan-2025

Controlled Document ID: CC Effective Date 31-Aug-2020

Sponsor: GlaxoSmithKline Research & Development Limited; Protocol No.: 214066/Protocol Amendment 02

- Other medical condition: nephrotic syndrome, diabetic renal disease, cystic kidney disease (autosomal dominant polycystic kidney disease [ADPKD], autosomal recessive polycystic kidney disease [ARPKD], nephronophthisis, other), traumatic loss of kidney, noninflammatory cause of failed kidney transplant, other.
- Hospitalization within 3 months prior to enrollment (Yes, No)
- Vascular access (Yes, No) and type (central venous catheter, central venous catheter nontunneled, arteriovenous fistula, arteriovenous graft)
- Duration of dialysis at screening in days, calculated as (Screening Date Dialysis Start Date) + 1.
- CKD Stage (Stage 3, Stage 4, Stage 5)

#### 9.5. Medical History

Medical histories are collected based on the pre-specified list of medical history terms provided in the electronic case report form (eCRF), where the sites have the option to enter any medical histories that are not covered in the pre-specified list, and these will be summarized under the category "Other". All medical histories will be categorized as past medical histories and current medical conditions based on the responses to the question "Ongoing at Screening", where past medical histories are those not ongoing at screening and current medical conditions are ongoing at screening. Medical history will not be summarized in any outputs.

#### 9.6. Concomitant Medication and Therapy

Concomitant medication or therapy is defined as any medication or therapy that the participant is receiving at the time of enrollment or receives during the study, including over-the-counter or prescription medicines, vitamins, and/or herbal supplements. All concomitant medications and therapies will be coded using WHO Drug Global B3 Sep 2024 or later (refer to Data Management Plan [DMP] for schedule of upversioning). All concomitant medications and therapies will be displayed in a listing for all enrolled participants for each sub-trial (D/ND), including all general medications, ESA therapies, blood products, and iron supplements.

#### 9.7. **Extent of Exposure**

Only enrolled participants may receive the study drug, in the form of either film-coated IR tablets or TfOS. Since the film-coated IR tablet and TfOS have similar formulations and tablet compositions, and the IR tablets and an oral solution had similar PK in previous studies, no dose adjustment between preparations is required. To support the correct dispensing of study drug for each study participant throughout the study, the IRT will be programmed with the starting dose based on their baseline status (age group, Hgb, ESA usage, and dialysis status) and any dose adjustment required based on their Hgb response to daprodustat.

The duration of the study drug will be calculated as (date of last dose – date of first dose + 1) / 7. Dose strength and dosing frequency will be documented in the databases, based on which the total amount of drug administered per treatment period (defined as the period between two scheduled study visits) can be calculated via the formula  $\sum_{t=1}^{T} Dose_t \times Freq_t$  where T is the total number of different dose strength and frequency combinations during the treatment period of interest. All relevant data will be displayed in a listing for each sub-trial (D/ND).

This document is confidential

SAP Version: SAP V1.0 23-Jan-2025

Controlled Document ID: CC Effective Date 31-Aug-2020

Sponsor: GlaxoSmithKline Research & Development Limited; Protocol No.: 214066/Protocol Amendment 02

# 9.8. Treatment Compliance

Overall treatment compliance is defined as [number of tablets dispensed – (number of tablets returned + number of tablets lost)] / number of tablets per day / (dose stop date – date start date + 1) × 100%. If there are dose changes during the course of the study, number of tablets per day used in the calculation will be the weighted average of the numbers of tablets per day with the weights being duration of each dose level, i.e., stop date at that dose level – start date at that dose level + 1. Similar method will be used to calculate treatment compliance per treatment period (defined as the period between two scheduled study visits). All relevant data used in calculating treatment compliance will be displayed in a listing for each sub-trial (D/ND).

This document is confidential.

SAP Version: SAP V1.0 23-Jan-2025

Controlled Document ID: CC Effective Date 31-Aug-2020 Filing requirements: TMF

Page 33 of 59

Statistical Analysis Plan for Interventional Studies

Sponsor: GlaxoSmithKline Research & Development Limited; Protocol No.: 214066/Protocol Amendment 02

# 10. Safety

The population used for safety analyses will be the Safety Set. Safety will be assessed based on AEs, clinical laboratory safety data, liver monitoring/stopping event, ECG parameters, height and weight, and vital signs. Planned time points for all safety assessments are listed in the Table 1 – Schedule of Activities. Additional time points for safety tests (such as vital signs, physical examinations and laboratory safety tests) may be added during the course of the study based on newly available data to ensure appropriate safety monitoring.

# 10.1. Adverse Events / Adverse Drug Reactions

An AE is any untoward medical occurrence in a clinical study participant, temporally associated with the use of the study intervention, whether or not considered related to the study intervention. All AEs will be coded using Medical Dictionary for Regulatory Activities (MedDRA) Version 27.0 or later (refer to the DMP for schedule of dictionary up-versioning) and will be summarized by system organ class (SOC) and preferred term (PT), or by SOC, PT and maximum intensity, or by PT alone as appropriate.

Per Section 7.1, all AEs will be handled using either treatment policy strategy or while-on-treatment strategy. Only death and kidney transplantation will be handled via while-on-treatment strategy where all AEs up to the occurrence of ICE will be included for analysis, whereas all other ICEs will be handled via treatment policy strategy where all AEs regardless of the occurrence of ICEs will be included for analysis.

## 10.1.1. Treatment-Emergent Adverse Events

Treatment-emergent adverse events (TEAEs) are those AEs with a start date on or after the commencement of daprodustat (Day 1) regardless of end dates. TEAEs will be summarized separately by SOC and PT. All AEs will be displayed in listings for each sub-trial (D/ND).

## 10.1.2. Adverse Events of Special Interest

The investigator or site staff will be responsible for detecting, documenting, and reporting any events that may represent the AESIs listed below:

- Death, myocardial infarction (MI), stroke, heart failure, thromboembolic events, thrombosis of vascular access.
  - Death
  - o MI
  - o Stroke
  - Heart failure
  - Thromboembolic event
  - Thrombosis of vascular access
- Thrombosis and/or tissue ischemia secondary to excessive erythropoiesis.
- New diagnosis of hypertension or worsening of existing hypertension
  - New diagnosis of hypertension
  - Worsening of existing hypertension
    - New resistant hypertension: hypertension despite treatment with at least 3 (maximal or maximally tolerated doses of) antihypertensive medications.
    - Hypertensive emergency: severely elevated BP associated with acute end-organ damage.

This document is confidential

SAP Version: SAP V1.0 23-Jan-2025

Controlled Document ID: CC Effective Date 31-Aug-2020

Sponsor: GlaxoSmithKline Research & Development Limited; Protocol No.: 214066/Protocol Amendment 02

- Hypertensive urgency: severely elevated BP without the presence of acute endorgan damage.
- Cancer related mortality and tumor progression and recurrence.
- Esophageal and gastric erosions

Potential AESIs will be identified through a pre-defined terms of interest process in which pre-defined lists of AE preferred terms corresponding with each AESI will be used to identify events considered to be potential AESIs. AESI definitions will be added once finalized. Sites will be prompted via query to complete any necessary additional information for these AESIs in the eCRF.

Thrombosis and tissue ischemia events will be considered to be secondary to excessive erythropoiesis if during the window of [AE start date – 30 days, AE start date +15 days] any one of the following 3 events occurs:

- Any Hgb value ≥ 13 g/dL (measured pre-dialysis)
- Hgb increase > 2 g/dL over 2 weeks (+1 week)
  - o Note: for programming purposes, a +1 week window is applied, corresponding to the allowable visit window, to look for increases > 2 g/dL over 3 weeks
- Hgb increase > 4 g/dL over 4 weeks (+1 week)
  - o Note: for programming purposes, a +1 week window is applied, corresponding to the allowable visit window, to look for increases > 4 g/dL over 5 weeks

To identify Hgb increases that meet the increase criterion above, all Hgb values taken within [AE start date – 58 days, AE start date + 15 days] will be identified. This corresponds to identifying Hgb values that occurred 4 weeks before the [AE start date – 30 days, AE start date +15 days] window of interest.

A summary table of AESIs by category, sub-categories, and PTs will be provided.

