### **Blood transfusions**

Blood transfusions should only be given if, in the opinion of the investigator, the benefit of transfusion outweighs the risks. Any blood transfusion (whole blood/packed red blood cells and number of units) should be recorded in the eCRF. Daprodustat can be continued at the current dose unless Hgb is >12.0 g/dL as a consequence of a blood transfusion, in which case according to Section 4.6, the daprodustat dose should be decreased (Hgb >12.0 to <12.5 g/dL) or withheld (Hgb >12.5 g/dL) and Hgb checked again at the

TMF-15144431 CONFIDENTIAL

214066 Protocol Amendment 02

next scheduled study visit or at an extra study visit within the next 4 weeks if a study visit is not due in that time frame.

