# 5.1. Primary Safety Endpoint

Incidence of Adverse Events (AEs), Serious Adverse Events (SAEs), Adverse Events of Special Interest (AESIs), and AEs leading to study intervention discontinuation for each sub-trial (D/ND).

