### 11.1.2. Handling of Unobserved Data

According Section 7.2, the following ICEs will be handled via while-on-treatment strategy.

- Permanent study intervention discontinuation due to any reason: any unobserved Hgb results
  after study intervention discontinuation will not be considered missing and will not be imputed;
  any observed Hgb results, if collected, will not be included for analysis.
- Unplanned use of ESA therapy: Hgb values within 8 weeks following the unplanned use of ESA
  therapy will be collected but will not be included in the analysis due to ESA's potential
  confounding effect on the interpretation of Hgb response; no imputation will be performed either.
- Intermittent use of rescue therapy (including use of iron supplements [oral/IV/both], blood transfusions and use of ESA and analogues): Hgb values from the date of initial use of rescue therapy until 8 weeks after the last dose of rescue therapy will be collected but will not be included in the analysis or imputed.
- Kidney transplantation or death: unobserved Hgb results after the event will not be considered
  missing and will not be imputed; any observed Hgb results, if collected, after kidney
  transplantation will not be included for analysis.

Disruption in study intervention, delays in study intervention, and transition to dialysis (for ND participants only) will be handled via treatment policy strategy where all observed Hgb results will be included for analysis, but no imputations will be performed for any missing Hgb results.

This document is confidential.

SAP Version: SAP V1.0 23-Jan-2025

Controlled Document ID: CC Effective Date 31-Aug-2020

Sponsor: GlaxoSmithKline Research & Development Limited; Protocol No.: 214066/Protocol Amendment 02

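### The SAP rule attributing thrombosis or ischemia to excessive erythropoiesis can be met through a red-cell transfusion, which can put an event in the wrong AESI category

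*SAP*

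**What the plan says.** SAP 10.1.2 sets the rule: "Thrombosis and tissue ischemia events will be considered to be secondary to excessive erythropoiesis if during the window of" 30 days before to 15 days after the event's start date any one of three Hgb triggers is met:

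- "Any Hgb value ≥ 13 g/dL (measured pre-dialysis");
- "Hgb increase > 2 g/dL over 2 weeks (+1 week"), programmed as 3 weeks;
- "Hgb increase > 4 g/dL over 4 weeks (+1 week"), programmed as 5 weeks.

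For the two rises, "all Hgb values taken within [AE start date – 58 days, AE start date + 15 days] will be identified". The section does not mention transfusion and has no adjudication step. Protocol 8.3.6 lists this AESI without defining it, so the SAP rule alone settles the category.

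The category feeds the primary endpoint, which includes "Adverse Events of Special Interest (AESIs), and AEs leading to study intervention discontinuation for each sub-trial (D/ND"), and Table 3.5 tabulates AESIs by category.

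On transfusion, Protocol 6.8.3 permits it at the investigator's discretion, accepts that it can take Hgb above 12.0 g/dL, and requires that "Any blood transfusion (whole blood/packed red blood cells and number of units) should be recorded in the eCRF". The estimand rationale in Protocol 3.2 says that rescue therapy may confound the reading of Hgb response. SAP 11.1.2 names blood transfusions as rescue and leaves out of the Hgb analysis "Hgb values from the date of initial use of rescue therapy until 8 weeks after the last dose of rescue therapy".

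**The concern.** The label states a mechanism, but the rule tests only a number. A transfusion raises Hgb without any need for increased red-cell production, so a qualifying value after packed cells is not evidence of that mechanism. Because the window runs 15 days past onset, a transfusion given after the event, perhaps because of it, can supply the event's recorded cause. For the Hgb endpoints the SAP regards the same values as too confounded to use, and neither document explains why they are acceptable here.

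At stake is how one AESI category is read. It is the first risk listed in Table 3 of the protocol, where the adult data give 25 of 3419 participants (0.7%). With a category this sparse, a few wrongly placed events would change its meaning.

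**Working it through.** **The plan's own figure.** The rule carries none. The only figure tied to the primary AE endpoint is the 90% chance of seeing at least one event at a rate of 3.76% with 60 participants (Protocol 9.5.2, SAP 4.3). It reproduces: 1 − (1 − 0.0376)^60 = 0.8997. It has no bearing on classification.

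**Inputs.** The triggers and windows come from SAP 10.1.2, and the 8-week (56-day) exclusion from SAP 11.1.2. Starting Hgb values are taken from the 7.0 to 11.0 g/dL entry range for ESA non-users (Protocol 5.1). The documents give no Hgb rise per transfusion, so rises of 1.0 to 4.1 g/dL were assumed.

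**Rule applied literally.** Two timings, in days relative to onset:

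- Transfusion before onset: Hgb at −14, transfusion at −10, Hgb at −2 (gap 12 days).
- Transfusion after onset: Hgb at −3, transfusion at +1, Hgb at +10 (gap 13 days).

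Both gaps are within 21 days, and both timings give the same results:

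| Hgb before → after (g/dL) | Rise | Triggers met as written | With 56 days after transfusion removed |
|---|---|---|---|
| 7.0 → 9.0 | 2.0 | none | none |
| 7.0 → 9.1 | 2.1 | >2 | none |
| 8.0 → 10.1 | 2.1 | >2 | none |
| 9.0 → 11.5 | 2.5 | >2 | none |
| 8.0 → 12.1 | 4.1 | >2, >4 | none |
| 9.0 → 13.1 | 4.1 | >2, >4, ≥13 | none |

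Rises of 1.0 and 1.5 g/dL also meet no trigger. The case ending at 9.1 g/dL never reaches the 10 to 12 g/dL target, and those ending at 10.1 and 11.5 finish inside it. In the last column the later value falls between transfusion and day +56, so no rise remains to be counted.

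**How often scheduled visits could show the rise.** From Week 4 to Week 28 visits are 28 days apart, each with a window of −7 to +2 days, so there are 10 × 10 = 100 pairs of integer offsets. The gap is 28 + (later offset − earlier offset), from 19 to 37 days.

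- A gap of 21 days or less needs the earlier offset to exceed the later by 7, 8 or 9: 3 + 2 + 1 = 6 pairs, or 6% if offsets are independent and uniform (an assumption).
- A gap of 35 days or less fails only when the later offset exceeds the earlier by 8 or 9: 2 + 1 = 3 pairs, leaving 97 of 100. That trigger, however, needs a rise above 4 g/dL.
- At 8-week spacing the smallest gap is 56 − 9 = 47 days, so two consecutive scheduled visits can meet neither rise trigger.

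After Week 4 the 2 g/dL trigger therefore rests mainly on unscheduled, extra or non-study Hgb. From Day 1 to Week 4 the scheduled visits are close enough to meet it.

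**Which AESI counts move.** MI, stroke, thromboembolic events and access thrombosis are already AESIs under the first category in SAP 10.1.2. For these the label adds a category row and leaves overall AESI incidence unchanged. Only an ischemia event outside that list would enter or leave the AESI count because of the label.

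**The case against.** The strongest reply is that this is a broad safety screen. SAP 7.1 and 10.1 handle rescue therapy by treatment policy, so events after transfusion are meant to count. The 8-week exclusion belongs to a different, secondary estimand. SAP 10.1.2 speaks of potential AESIs, leaves AESI definitions to be finalized and has sites queried. Events, blood products and all Hgb values are listed (Listings 16.9, 16.15 and 16.17), so with only 4 participants enrolled (population PK analysis plan, Section 1.1) any labeled case can be checked by eye.

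Part of this stands. A reader might infer that SAP 10.1.2 and 11.1.2 contradict each other outright. They do not, because they serve different estimands; what is missing is a reason for the difference. A reader might also infer that the label attributes the event to daprodustat. The SAP does not say so, and drug causality is a separate investigator assessment (Protocol 10.3.3). Nor can it be said that no erythropoiesis occurred in a transfused participant who is also taking daprodustat; the point is only that the rule does not require any.

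The rest does not answer the point. Treatment policy keeps the event in the analysis but does not justify its stated mechanism. The pending definitions follow the sentence on preferred-term lists, while the Hgb criteria are already fixed in the text. Listings let a careful reader spot a wrong category but do not correct Table 3.5.

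**Conclusion.** Wrong as written, with limited reach. The rule can give the excessive-erythropoiesis label to an event whose qualifying Hgb level or rise follows a red-cell transfusion, including one given up to 15 days after onset. This needs a thrombosis or ischemia event together with Hgb of at least 13 g/dL, or a rise above 2 g/dL within 3 weeks or above 4 g/dL within 5. The size of transfusion rises is an assumption here, and no actual case is shown.

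Three stronger readings are tempting and unsupported:

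- That transfused participants are misclassified as a matter of course. Most would meet no trigger unless a qualifying event and rise coincided.
- That the primary endpoint as a whole is biased. The damage is mainly to one category row.
- That 1/60 = 1.7 or 1/4 = 25 percentage points measures the error. Those are the weight of any single event at the planned 60 per sub-trial or the 4 enrolled. The documents allow no estimate of how often misclassification would occur.

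**What to change.** In SAP 10.1.2, evaluate the three Hgb criteria twice: once on all values, and once leaving out values taken after a red-cell transfusion and within the SAP's own 8-week window. Split the Table 3.5 category into 'criterion met without post-transfusion Hgb' and 'criterion met only with post-transfusion Hgb', and attribute only the first to excessive erythropoiesis. State how an Hgb dated the same day as a transfusion is treated.

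This is better than removing the label for 56 days, because daprodustat can continue after a transfusion and a true overshoot should not disappear. The cost is a few lines of SAP text, one date check and one extra table row. Transfusions are already recorded in the eCRF, linked to the concomitant medication log (SAP 13.1) and listed (SAP 9.6). The small downside is that true overshoot soon after a transfusion would fall in the second row, but it stays visible and no event is lost.
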